9.2. Adverse Events

Subjects with any AE(s) will be tabulated by type of AE(s) and number of enrolled eyes for each actual treatment received and total drug (i.e., the combination of DE-109 440 μ g and DE-109 fixed dose arm). Study eyes with any ocular AE(s) will be tabulated by type of AE(s) for each actual treatment received and total drug. For subject-level summaries, any AEs experienced by either eye or both eyes will be counted once for that AE. Unless specified otherwise, ocular AEs in study eyes will be summarized at the eye-level, while overall AEs, ocular AEs in fellow eyes, and non-ocular AEs will be summarized at the subject-level.

Besides the overall AE summary, AEs, SAEs, ADRs, serious ADRs will be tabulated by SOC and preferred term for all AEs, ocular AEs, and non-ocular AEs separately. A subject/study eye which experienced multiple AEs within a SOC or preferred term will be counted only once for that SOC or preferred term for subject-level/eye-level summaries. Non-serious AEs (including number of events) will also be summarized by SOC and preferred term. ESIs will be summarized descriptively at the eye-level.

AEs, SAEs, ADRs, serious ADRs, ocular AEs, AEs leading to death, AEs leading to study drug discontinuation, and ESIs, if any, will be listed separately.

9.3. Intraocular Pressure

IOP and change from baseline in IOP will be summarized by analysis visit.

Change after injection in IOP will be summarized by injection visit. Subjects with any increase of ≥ 10 mmHg in IOP after injection will be listed.

9.4. Slit-lamp Biomicroscopy

For each biomicroscopy parameter rated on a 0-3 scale (0=None, 1=Mild, 2=Moderate, 3=Severe), rating scores and changes from baseline will be summarized by analysis visit for study eyes and fellow eyes, separately. In addition, any worsening (increase) of ≥ 2 units from baseline will be listed. Any clinically significant worsening from baseline in severity will also be listed.

For lid hyperemia, lid edema, conjunctival hyperemia, chemosis, corneal edema, conjunctival discharge/exudate, and anterior chamber flare, shift from baseline in severity rating score will be summarized by analysis visit and shift after injection will be summarized by injection visit. Subjects with any clinically significant abnormality will be listed by biomicroscopic parameter. In addition, subjects with any worsening (increase) of 2 units or more from baseline will also be listed by biomicroscopic parameter.

For pupil, lashes, ocular motility, and iris, shift from baseline in status (Normal or Abnormal) will be summarized by analysis visit and shift after injection will be summarized by injection visit. Subjects with any clinically significant abnormality will be listed by biomicroscopic parameter. In addition, subjects with any change from Normal at baseline to Abnormal in status will also be listed by biomicroscopic parameter.

For vitreous cell count and anterior chamber cells, shift from baseline in rating score will be summarized by analysis visit and shift after injection will be summarized by injection visit.

9.4.1. Lens

For phakic lens only, shift from baseline in cataract severity score will be summarized by analysis visit and shift after injection will be summarized by injection visit. Subjects with any worsening (increase) of 2 units or more from baseline in cataract severity will be listed. In addition, subjects with any cataract that affected grading of degree of inflammation will also be listed.

9.5. **Ophthalmoscopy**

For retina vessels, macula, fovea, periphery, and optic nerve, shift from baseline in status (Normal or Abnormal) will be summarized by analysis visit and shift after injection will be summarized by injection visit. Subjects with any change from Normal at baseline to Abnormal in status will be listed by ophthalmoscopic parameter.

For vitreous hemorrhage, retinal detachment, and retinal tear, shift from baseline in presence status (None or Present) will be summarized by analysis visit and shift after injection will be summarized by injection visit. Subjects with any change from None at baseline to Present in presence status will be listed by ophthalmoscopic parameter.

For cup/disc ratio, score and change-from-baseline score will be summarized by analysis visit. Change after injection in cup/disc ratio will be summarized by injection visit. Subjects with any worsening (increase) of 0.2 units or more from baseline in cup/disc ratio will be listed.

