8.2.13. Events of Special Interest

Events of Special Interest (ESIs) are medical events both anticipated and unanticipated that may have particular impact on the benefit/risk profile of DE-109 and therefore may require more detailed characterization. The DE-109 Investigational Brochure is the source for defining the DE-109 ESIs and should be consulted for further information.

The DE-109 ESIs are specific to the study eye only and are as follows:

- Clinically significant new or worsening of uveitis, defined as satisfaction of any of the following:
 - Worsening of uveitis in the study eye as indicated by at least a 2-step increase in VH score (i.e., 0 to ≥ 2+, 0.5+ to ≥ 3+, 1+ to ≥ 3+, 1.5+ to ≥ 4+, or 2+ to ≥ 4+) as compared to the baseline (Day 1) VH score or the best achieved VH score postbaseline.
 - Severe deterioration of vision in the study eye due to worsening of uveitis that is indicated by at least doubling of the visual angle (loss of 3 or more lines [≥15 ETDRS letters]) as compared to baseline (Day 1) BCVA.
 - New or worsening retinal or choroidal uveitic lesion(s) in the study eye as compared to baseline (Day 1).
 - New or worsening uveitis otherwise deemed clinically significant by the investigator in the study eye as compared to the baseline (Day 1).

Note: When documenting clinically significant new or worsening uveitis, the anatomic location (e.g., anterior uveitis, intermediate uveitis, posterior uveitis, or panuveitis) should be specified.

- Endophthalmitis / Sterile Endophthalmitis in the study eye A guided questionnaire is provided as part of the eCRFs to facilitate the documentation of endophthalmitis and sterile endophthalmitis. Endophthalmitis is also to be reported as an SAE (Section 10.4).
- Traumatic cataract in the study eye
- Vitreoretinal hemorrhage in the study eye
- Drug depot in visual axis in the study eye
- Retinal detachment (also to be reported as an SAE, Section 10.4) in the study eye
- Increased IOP (> 10 mmHg as compared to baseline). Note that certain instances of increased IOP are to be reported as an SAE (IOP >35 mmHg that persists for at least 7 days despite pharmacologic therapy, Section 10.4) in the study eye.
- Cataract (new or worsening from baseline) in the study eye
- Investigational product administration error considered to be significant by the investigator (examples include administration of IP from an incorrect kit and IP administration error attributed to some aspect of the instructions provided)

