5.2.2. Safety Measures

Descriptive summaries of safety measures will be based on observed data only. No imputation of missing scores will be implemented.

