9.1.2. Safety Measures

Table 3 lists the safety measures to be evaluated for this study.

Table 3:	Safety Assessments
----------	--------------------

Safety Measures	Note
Slit-lamp biomicroscopy: vitreous, eyelid, conjunctiva, cornea, anterior chamber cells and flare, iris and pupil, ocular motility	The status of each of these biomicroscopy parameters was determined as Normal or Abnormal. For each abnormal record, the parameter was rated as $1 = Mild$, $2 = Moderate$, or $3 = Severe$.
Slit-lamp Biomicroscopy: vitreous cell count	This measure was rated as $0 = 0$ cells, $0.5+=1-10$ cells, $1+=11-20$ cells, $2+=21-30$ cells, $3+=31-100$ cells, $4+=>100$ cells
Slit-lamp Biomicroscopy: anterior chamber cells	This measure was rated as $0 = 0$ cells, $0.5+=1-5$ cells, $1+=6-15$ cells, $2+=16-25$ cells, $3+=26-50$ cells, $4+=>50$ cells
Slit-lamp Biomicroscopy: anterior chamber flare	This measure was rated as $0 = None$, $1 + = Faint$, $2 + = Moderate$, $3 + = Marked$, $4 + = Intense$
Slit-lamp Biomicroscopy: lens and cataract	The lens of an eye was classified as Phakic, Aphakic, or Pseudophakic. For phakic lens with cataract, the severity was rates as $1 = Mild$, $2 = Moderate$, $3 = Severe$. In addition, whether cataract affects grading of degree of inflammation (Yes or No) was also determined.
Intraocular pressure	The IOP, the fluid pressure inside the eye, was recorded in mmHg with one decimal point (e.g., 24.0 mmHg). For this study, the elevated IOP, depending on the level of elevation, might be reported as an AE at Clinical Investigator's discretion.
Indirect ophthalmoscopy: retina vessels, macula, fovea, periphery, optic nerve, cup-to- disc ratio	The status of retina vessels, macula, fovea, periphery, and optic nerve was determined as Normal or Abnormal. The cup-to-disc ratio was recorded with two decimal points (e.g., 0.80)
Best-corrected visual acuity (BCVA)	BCVA measures the acuteness or clearness of best-corrected vision, with a range of [0, 110] in ETDRS letters. An increase in BCVA indicates improvement in the best-corrected vision. A 5-letter difference in visual acuity is equivalent to one Snellen line. A BCVA score of 85 ETDRS letters is equivalent to 20/20 vision, which is considered normal vision.
Central Subfield Thickness (CST)	For each eye, the CST was measured using Optical Coherence Tomography (OCT). OCT was performed using reading center certified photographers, equipment, and standardized protocols.

Safety Measures	Note

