Physical examination: Height, weight	The physical exam result was determined as Normal, Abnormal, or No Change. The weight and the height were recorded with one decimal point in inch/cm and lb/kg, respectively. The conversion rules "1 lb = 0.453592 kg" and "1 in = 2.54 cm" will be followed to convert lb to kg and into cm, respectively.
Vital signs: Oral temperature, systolic and diastolic blood pressure, heart rate	The oral temperature was recorded in °F or °C. The conversion rule "°C = $5/9 \times (°F - 32)$ " will be followed to convert °F to °C. The blood pressure (systolic and diastolic) and the heart rate were recorded in mmHg and beats per minute (bpm), respectively.
Laboratory tests: Blood chemistry/hematology, urinalysis	The minimum blood and urine parameters collected in the study are listed in Appendix B. Hematology, chemistry, and urinalysis outcomes were determined by the Clinical Investigator as Normal, Not Clinically Significant Abnormality or Clinically Significant Abnormality based on the
	comprehensive review of the relevant laboratory test results.

 Table 3:
 Safety Assessments (Continued)

The safety-related measures collected in this study include AEs, events of special interest (ESIs), slit-lamp biomicroscopy findings, IOP, best-corrected visual acuity, indirect ophthalmoscopy findings, central subfield thickness, physical exam results, vital signs, and laboratory test results. The Safety population will be used for all summaries.

All the safety-related measures will be summarized descriptively by actual treatment received. Except AEs, the descriptive summary of each ocular safety-related measurement and the change from baseline in that measure will be performed for study eyes and fellow eyes separately.

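### Eyes that have cataract extraction on study leave the later cataract shift tables, and the cataract event summary has no phakic-at-baseline denominator

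*SAP*

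**What the plan says.** SAP 9.4.1 (Lens): "For phakic lens only, shift from baseline in cataract severity score will be summarized by analysis visit". A shift after injection is added by injection visit. The section does not say whether phakic is judged at baseline or at the visit. It also plans a listing: "Subjects with any worsening (increase) of 2 units or more from baseline in cataract severity will be listed".

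SAP 9.1.2, Table 3: "The lens of an eye was classified as Phakic, Aphakic, or Pseudophakic". The grade of 1 to 3 is tied to one of these states: "For phakic lens with cataract, the severity was rates as" mild, moderate or severe. An aphakic or pseudophakic eye has no grade.

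SAP 5.2.2: "Descriptive summaries of safety measures will be based on observed data only. No imputation of missing scores will be implemented".

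Protocol 8.2.13 names as an event of special interest (ESI): "Cataract (new or worsening from baseline) in the study eye". SAP 9.1.1.5 repeats it, and both list traumatic cataract separately. On reporting, SAP 9.2 says "ESIs will be summarized descriptively at the eye-level", and ESIs are also listed. SAP 9.1.2 adds: "The Safety population will be used for all summaries". Under SAP 6.1 that population, at eye level, is every study eye given at least one administration, whatever its lens status.

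Non-phakic eyes can be study eyes. Protocol Table 6 recommends a separate injection entry site for aphakic and pseudophakic subjects, and no exclusion criterion in Protocol 5.2 removes such eyes. Lens status is not among the baseline variables named in SAP 7.2.

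**The concern.** Two features of the plan pull the cataract figures downward.

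First, removal from the shift table is caused by the outcome that the table is meant to show. An eye whose cataract progresses to extraction is a clear case of progression, yet after surgery it has no grade and no category to sit in. The later the visit, the more such eyes may have gone.

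Second, an eye without its natural lens at baseline cannot newly develop cataract. Counting it in the denominator lowers the reported rate, and if the arms differ in the share of such eyes, it also changes the comparison between them. Without a planned table of baseline lens status, a reader of the report may be unable to see or correct this.

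Cataract is one of the events that the protocol singles out for the benefit/risk profile of DE-109, and Protocol 2.2 cites cataract as a drawback of existing corticosteroid therapy. The reported rate will therefore be read closely.

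**Working it through.** The plan states no cataract rate, surgery count or lens-status share, so there is no figure of its own to reproduce here. The check is a reading of the rules, followed by an illustration under assumed inputs.

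**Step 1: what happens to an operated eye.** Take a study eye that is phakic at baseline and has extraction before a later visit.
- If phakic means at the visit, SAP 9.4.1 excludes the eye from that visit's table.
- If phakic means at baseline, the eye is eligible, but Table 3 gives it no grade after surgery and SAP 5.2.2 fills nothing in.

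Either way the eye is absent from that table and all later ones. No planned summary of lens status by visit, or of cataract surgery, replaces it.

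**Step 2: effect on the shift table (assumed inputs).** Suppose one eye per subject, 80 subjects in an arm and 30% non-phakic at baseline: 80 × 0.70 = 56 eyes phakic at baseline. Suppose 6 of these worsen and k of the 6 are operated on.

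Share shown as worsened = (6 − k) / (56 − k)

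| k operated | Shift table as planned | Operated eyes kept as worsened |
|---|---|---|
| 0 | 6/56 = 10.7% | 6/56 = 10.7% |
| 1 | 5/55 = 9.1% | 6/56 = 10.7% |
| 3 | 3/53 = 5.7% | 6/56 = 10.7% |
| 5 | 1/51 = 2.0% | 6/56 = 10.7% |

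**Step 3: effect on the ESI rate (assumed inputs).** With rate r in eyes phakic at baseline and non-phakic share s:

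Rate over all treated study eyes = r × (1 − s)

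For r = 10%:

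| s | Rate over all treated study eyes |
|---|---|
| 10% | 9% |
| 20% | 8% |
| 30% | 7% |
| 40% | 6% |
| 50% | 5% |

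With eyes phakic at baseline as denominator the rate stays at 10%.

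**Step 4: effect of an imbalance between arms (assumed inputs).** Keep the same 10% rate in phakic eyes in both arms, and let 20% of eyes in one arm and 40% in the other be non-phakic. The all-eye rates are 10% × 0.80 = 8% and 10% × 0.60 = 6%, a 2-point difference produced by lens status alone.

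**The case against.** The strongest reply is that the worst cases leave one display, not the safety analysis. That is right. A reader might infer from SAP 9.4.1 that the shift table is the only analysis of the lens, but SAP 9.2 tabulates adverse events by system organ class and preferred term, and summarizes and lists ESIs. The cataract ESI has no grade threshold. Protocol 10.4 treats the condition leading to a procedure as the adverse event, so an operated eye should be counted there.

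Three further readings are tempting, and the documents do not support them:
- That a new cataract has no baseline score to shift from. Table 3 indeed gives no value for a clear lens, but the parent section, SAP 9.4, defines its 0 to 3 scale with 0 as none. The natural reading is that this covers the lens; one clarifying phrase settles it.
- That one-grade changes are missed. The 2-unit threshold governs a listing only. A shift table shows one-grade moves, SAP 9.4 also lists clinically significant worsening, and every cataract ESI is listed.
- That the distortion affects a 12-month comparison with sham. Sham control ends at Month 6, after which all subjects receive DE-109 440 µg.

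On frequency, exclusion 7a in Protocol 5.2 removes eyes whose lens opacity could need surgery during a 5-month period. This should make extraction uncommon through most of the sham-controlled period. It gives less assurance up to Month 12.

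On the denominator, using the Safety population is ordinary practice, SAP 9.2 names no rate, and randomization balances lens status in expectation. Equal dilution leaves the ratio of rates unchanged. These points stand. They do not help with the absolute rate, which is still lowered, or with a chance imbalance. SAP 7.2 permits other baseline variables and SAP 7.3 tabulates eye-disorder history in study eyes, but neither commits to a table of lens status.

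**Conclusion.** The concern holds for descriptive safety reporting. Under the rules as written, an eye with on-study extraction disappears from later cataract shift tables because of its outcome, whichever way phakic is read. The cataract ESI summary falls by default on all treated study eyes. The SAP does not state that denominator for the ESI itself; it follows from applying the Safety population to all safety summaries.

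The direction is understatement, but the size cannot be fixed from the documents. It depends on how many eyes are operated on and how many are non-phakic at baseline, and the percentages in the working are illustrations under assumed values. Few operations and a small, balanced non-phakic share would make the effect slight.

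No hypothesis test is planned for safety. The primary and key secondary analyses and the sample size are untouched. This is a worthwhile, inexpensive improvement and not a flaw in the trial's main conclusions.

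**What to change.** - **SAP 9.4.1:** define the shift-table set as study eyes phakic at baseline. Carry an on-study change to pseudophakic or aphakic as a separate worst category at that visit and every later one. State that a lens without cataract is coded 0, in line with SAP 9.4.
- **SAP 9.2:** alongside the existing summary, present cataract ESIs with study eyes phakic at baseline as the denominator.
- **SAP 7.2:** tabulate baseline lens status by arm.

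The cost is SAP wording, one derived lens-category variable and a few extra table rows. No new data are needed, because Protocol 8.2.1 already has lens and cataract status assessed at slit-lamp examinations. Treatment and clinical management do not change. The downside for the sponsor is a slightly higher reported cataract rate.

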9.6. Physical Examination and Vital Signs

For weight, height, oral temperature, blood pressure, and heart rate, score and change from baseline score will be summarized by analysis visit. Subjects with any change from Normal at baseline to Abnormal in physical exam result will be listed.

9.7. Laboratory Tests

Hematology results will be summarized by laboratory test and analysis visit. Subjects with any clinically significant abnormality in hematology will be listed.

10. SUMMARY OF CHANGES TO THE PROTOCOL

10.1. Adding Exploratory Endpoints

The visual acuity-related endpoints (presented in Section 2.3.5) were added to explore the treatment effect of DE-109 440 μ g among Macular Edema population subjects.

10.2. Adding Exploratory Analyses

In previous studies, DE-109 has showed some evidence of efficacy across different doses. To further explore the overall efficacy of DE-109, the analysis of primary endpoint and the analyses of key secondary endpoints will be repeated on the combined DE-109 μ g and DE-109 fixed dose arms versus Sham arm.

Analysis of BCVA-related endpoints was also added in corresponding to the added exploratory endpoints.

11. **REFERENCE**

- 1. Kenward, M. G., Roger, J. H. (1997). Small Sample Inference for Fixed Effects from Restricted Maximum Likelihood. Biometrics. 53(3):983-97. PubMed PMID: 9333350.
- 2. Mehta, C. R., Pocock, S. J. (2011). Adaptive increase in sample size when interim results are promising: a practical guide with examples. Stat Med. 30(28):3267-84.

APPENDIX A. VFQ-25 COMPOSITE SCORE AND SUBSCALES

Following steps will be taken to derive the VFQ-25 composite score and subscales:

Step One: Recode Item Scores

Item Numbers on VFQ-25	Original Response ^a	Recode Value
1, 3, 4	1	100
	2	75
	3	50
	4	25
	5	0
2	1	100
	2	80
	3	60
	4	40
	5	20
	6	0
5, 6, 7, 8, 9, 10, 11, 12, 13, 14, 16, 16a, A3 ^b , A4 ^b , A5 ^b , A6 ^b ,	1	100
$A7^{b}, A8^{b}, A9^{b}$	2	75
	3	50
	4	25
	5	0
	6	*c
15c ^d	1	100
	2	75
	3	50
	4	25
		0
17, 18, 19, 20, 21, 22, 23, 24, 25, A11a ^b , A11b ^b , A12 ^b , A13 ^b	1	0
	2	25
	3	50
	4	75
	5	100
A1 ^b , A2 ^b	0	0
	to	to
	10	100

^a Original response choices as printed in the questionnaire

^b The letter "A" before the item number indicates that this item is an optional item from the Appendix of VFQ-25 questionnaire.

^c A response of '6' indicates that the person does not perform the activity because of non-vision related problems. If '6' is selected, the item will be recoded as missing.

^d Item 15c has 4 levels (1, 2, 3, or 4), but it is recoded to 5 levels by incorporating the response choice for Item 15b: if 15b = 1 then 15c is recoded to 0;

if 15b = 2 or 3 then 15c is recorded to missing.

Score or Subscale	Items to be averaged (after step 1)
General Health	1, A1
General Vision	2, A2
Ocular Pain	4, 19
Near Activities	5, 6, 7, A3, A4, A5
Distance Activities	8, 9, 14, A6, A7, A8
Vision Specific Social Functioning	11, 13, A9
Vision Specific Mental Health	3, 21, 22, 25, A12
Vision Specific Role Difficulties	17, 18, A11a, A11b
Vision Specific Dependency	20, 23, 24, A13
Driving	15c, 16, 16a
Color Vision	12
Peripheral Vision	10
Composite Score	All items except Item 1 and A1

Step Two: Identify Items Needed to Derive VFQ-25 Composite Score and Subscales

Step Three: Derive VFQ-25 Composite Score and Subscales

Score = Sum of all items with a non-missing answer / Total number of items with a non-missing answer, with a range of [0, 100] (0 = Worst possible score; 100 = Best score)

APPENDIX B. CLINICAL LABORATORY PARAMETERS

Serum Chemistry and Hematology

The following is a list of the minimum parameters that will be measured. Other additional parameters may also be reported.

Table 4:	Serum	Chemistry	and	Hematology

Chemistry	Hematology
Albumin	red blood cells (RBC)
Creatinine	white blood cells (WBC)
lactate dehydrogenase (LDH)	differential WBC
Glucose	platelets (PLT)
Calcium	hemoglobin (HGB)
Potassium	hematocrit (HCT)
Sodium	mean corpuscular volume (MCV)
cholesterol (total, HDL and LDL)	mean corpuscular hemoglobin (MCH)
Triglycerides	mean corpuscular hemoglobin conc. (MCHC)
urea nitrogen	
bilirubin (total, direct, indirect)	
alkaline phosphatase (ALP)	
alanine aminotransferase (ALT)	
aspartate aminotransferase (AST)	
gamma glutamyl transferase (GGT)	

Urinalysis

The following is a list of the minimum urine parameters that will be measured. Other additional urine parameters may also be reported.

|--|

Confidential
